9. RESEARCH METHODS

9.1. Study design

The study will be a non-interventional, descriptive, and longitudinal prospective study with primary data collection that involves sites/investigators. The patients must be diagnosed before enrollment with ATTR-CM and prescribed with tafamidis following indications approved by National Institute for Drug and Food Vigilance (INVIMA) in Colombia. The patients will be followed up from the index date until patient i) have deceased, ii) have decided to withdraw from the study, iii) have terminated of treatment, iv) have been lost to follow up, or, v) finalize the 24 months of following up, the event that happens first. The index date will be defined as the date for the first prescription of tafamidis.

The patients that were prescribed with tafamidis before August of 2023 will be recruited. In the cases where the patients were prescribed before starting the study, all previous information will be collected from the data provided by the patients. The quality of life will be evaluated when the patient accepts to participate and signs the informed consent.

Quality of life, adherence, concomitant treatment, hospitalization for any causes, cardiovascular functionality will be measured 24 months after the prescription of tafamidis. Twelve months before the index date, treatments, and frequency of hospitalization for any causes will be measured (Table 1).

There will be two sources of information. Clinical and demographic information and death at the baseline will be abstracted from the medical record while the data related to hospitalizations, cardiovascular functionality, quality of life will be collected directly from the patients using validated questionnaires and structured interviews. Thus, in this case the report form (CRF) will serve as a source document.

In patients who have been prescribed with tafamidis more than 1 month and have not received the drug by the HMO yet, the first time of administration of tafamidis will be considered in the analysis. It will be considered as limitation of access. Any delay of supply for treatment will be considered limitation of access which will be assessed during the follow-up.

The scale of quality of life named Kansas City Cardiomyopathy Questionnaire (KCCQ) (12) will be used after the acceptance to participate in the study by the patients with the signing of informed consent. In the statistical analysis will be considered the date to start tafamidis, the date of prescription of tafamidis and the time to start the measurement of QoL.

Data collection will be conducted with a CRF. This will be validated by two research centers to ensure feasibility of data collection, availability of the data as well as source documents and accurate definition of the study variables. The research staff at the participating centers will be trained in data extraction and completion of CRF.

The patients will be reached out to every three months±15 days through a phone call by a healthcare professional of the site. During this interview, the professional will perform a

PFIZER CONFIDENTIAL

CT24-WI-GL02-RF01 6.0 Non-Interventional Study Protocol Template For Primary Data Collection Study 01-

Aug-2023

Page 21 of 57

**CLINICAL AND MEDICAL CONTROLLED DOCUMENT (CMCD)
REQUIRED FORM/TEMPLATE**

Identifier	Version	Title	Effective Date
CT24-WI-GL02-RF01	6.0	NON-INTERVENTIONAL STUDY PROTOCOL TEMPLATE FOR PRIMARY DATA COLLECTION STUDY	01-Aug-2023

standardized interview with structured questionnaires to guarantee that the data collection process will be harmonized among patients. The interview could be in the site, if the patient received clinical care in there or she decided to move to it. Both collection data are completely accepted in the study.

The 6 min walk test (6MWT) and scintigraphy will be conducted based on the decision of cardiologist or responsible physician based on the guideline of the institution or medical practice. This study does not suggest these tests or is limited to them. They will be abstracted from medical records of patients who had measured them (13).

All assessments described in this protocol will be performed as part of normal clinical practice or standard practice guidelines for the patient population and healthcare provider specialty in Colombia where this noninterventional study is being conducted.

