The study will be a non-interventional, descriptive, and longitudinal prospective study with primary data collection that involves sites/investigators. The patients must be diagnosed before enrollment with ATTR-CM and prescribed with tafamidis following the indications approved by National Institute for Drug and Food Vigilance (INVIMA) in Colombia. The patients will be followed up from the index date until patient i) have deceased, ii) have decided to withdraw from the study, iii) have terminated of treatment, iv) have been lost to follow up, or v) finalize the 24 months of following up. The index date will be defined as the date for the first prescription of tafamidis.

The patients who have been prescribed with tafamidis before August of 2023 will be recruited. The quality of life will be evaluated when the patient accepts to participate and signs the informed consent.

Quality of life, adherence, concomitant treatment, hospitalization for any causes, cardiovascular functionality will be measured 24 months after the prescription of tafamidis. Twelve months before the index date, treatments, and frequency of hospitalization for any causes will be measured (Table 1).

PFIZER CONFIDENTIAL

CT24-WI-GL02-RF01 6.0 Non-Interventional Study Protocol Template For Primary Data Collection Study 01-

Aug-2023

Page 11 of 57

**CLINICAL AND MEDICAL CONTROLLED DOCUMENT (CMCD)
REQUIRED FORM/TEMPLATE**

Identifier	Version	Title	Effective Date
CT24-WI-GL02-RF01	6.0	NON-INTERVENTIONAL STUDY PROTOCOL TEMPLATE FOR PRIMARY DATA COLLECTION STUDY	01-Aug-2023

There will be two sources of information. Clinical and demographic information at the baseline will be abstracted from the medical record while the data related to hospitalizations, cardiovascular functionality, quality of life, and deaths will be collected directly from the patients using validated questionnaires and structured interviews. Thus, in this case the report form (CRF) will serve as a source document.

The patients will be reached out to every three months±15 days through a phone call by a healthcare professional of the site. During this interview, the professional will perform a standardized interview with structured questionnaires to guarantee that the data collection process will be harmonized among patients. The interview could be in the site if the patient received clinical care there or she decided to move to it. Both collection data are completely accepted in the study.

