8. RESEARCH QUESTION AND OBJECTIVES

Hypothesis

There are not hypotheses to evaluate.

Research Question

What is the impact of tafamidis use in Colombian patients diagnosed with ATTR-CM on quality of life during two years of follow-up?

Primary objective

To describe the impact of tafamidis use in Colombian patients diagnosed with ATTR-CM on quality of life during two years of follow-up

Secondary objectives

- To describe the clinical and demographic characteristics of the patients at the moment of prescription of tafamidis
- To determine the treatment patterns to manage ATTR-CM before tafamidis prescription
- To evaluate the frequency of hospitalization and its causes during the follow-up period
- To describe the use of cardiovascular devices during follow-up of patients recruited in the study
- To outline the change in baseline for patients in cardiovascular functionality in patients prescribed tafamidis
- To measure the adherence of the patients to the therapy
- To describe the access barriers during the use of tafamidis

Exploratory objectives

- To analyze the relationship between baseline variables and patient and changes of quality of life and cardiovascular functionality

PFIZER CONFIDENTIAL

CT24-WI-GL02-RF01 6.0 Non-Interventional Study Protocol Template For Primary Data Collection Study 01-Aug-2023
Page 20 of 57

CLINICAL AND MEDICAL CONTROLLED DOCUMENT (CMCD) REQUIRED FORM/TEMPLATE

Identifier	Version	Title	Effective Date
CT24-WI-GL02-RF01	6.0	NON-INTERVENTIONAL STUDY PROTOCOL TEMPLATE FOR PRIMARY DATA COLLECTION STUDY	01-Aug-2023

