9.2. Setting

The study will be performed in approximately 6 Colombian Health Provider Institution (IPS, in its Spanish acronym) whose population includes patients with ATTR-CM diagnosis in the period established. These sites will be in four Colombian cities (Bogotá, Medellin, Cali, and Barranquilla) which have a cardiologist with experience in diagnostic and management of ATTR-CM. The patients can be recruited from the same site or other healthcare institutions, which the site affiliated to the study can invite to participate. In this last scenario, the patients will maintain the clinical care of the original institution, but the information of the study will be collected in the sites affiliated to the study or by their healthcare professionals through virtual interview.

Tafamidis was approved in July 2022 by INVIMA in the treatment of ATTR-CM (14), thus, the patients with diagnosis of ATTR-CM and treated with tafamidis between August 2022 to August 2023 will be invited to participate in the study. At this time, the number of patients expected to participate will be less than 50 patients considering the number of patients diagnosed with ATTR-CM. This cohort study its representative to patients in Colombia without requiring sampling method, considering the estimated number of patients diagnosed with this disease under treatment with tafamidis.

The follow-up period is 24 months since index date with measurement every three months \pm 15 days. During this period quality of life, hospitalization frequency, and death will be measured. The endpoint of the study will be death. Additionally, adherence will be measured. For the cardiovascular functionality, it will be abstracted from the medical records 6MWT and scintigraphy during the time of study.

The activities will be included in the following table.

PFIZER CONFIDENTIAL

CT24-WI-GL02-RF01 6.0 Non-Interventional Study Protocol Template For Primary Data Collection Study 01-

Aug-2023

Page 22 of 57

**CLINICAL AND MEDICAL CONTROLLED DOCUMENT (CMCD)
REQUIRED FORM/TEMPLATE**

Identifier	Version	Title	Effective Date
CT24-WI-GL02-RF01	6.0	NON-INTERVENTIONAL STUDY PROTOCOL TEMPLATE FOR PRIMARY DATA COLLECTION STUDY	01-Aug-2023

Table 1 List of activities

Visit Identifier	Screening	Month ± 15 days										End of Observation
		-12	0	3	6	9	12	15	18	21	24	
Visit Window												
Informed consent	X											
Medical history	X											
Demographic		X										
Clinical variable		X										

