10.3. Patient withdrawal

Patients may withdraw from the study at any time at their own request, or they may be withdrawn at any time at the discretion of the investigator or sponsor for safety, behavioral, or administrative reasons. In any circumstance, every effort should be made to document patient outcome, if applicable. The investigator would inquire about the reason for withdrawal and follow-up with the patient regarding any unresolved adverse events.

If the patient withdraws from the study, and also withdraws consent for disclosure of future information, no further evaluations should be performed, and no additional data should be collected. The sponsor may retain and continue to use any data collected before such withdrawal of consent.

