previously forwarded safety event reports. In the rare situation that the investigator does not become immediately aware of the occurrence of a safety event, the investigator must report the event within 24 hours after learning of it and document the time of his/her first awareness of the events.

For safety events that are considered serious or that are identified in the far-right column of the table above that are reportable to Pfizer within 24 hours of awareness, the investigator is obligated to pursue and to provide any additional information to Pfizer in accordance with this 24-hour timeframe. In addition, an investigator may be requested by Pfizer to obtain specific follow-up information in an expedited fashion. This information is more detailed than that recorded on the CRF. In general, this will include a description of the AE in sufficient detail to allow for a complete medical assessment of the case and independent determination of possible causality. Any information relevant to the event, such as concomitant medications and illnesses, must be provided. In the case of a patient death, a summary of available autopsy findings must be submitted as soon as possible to Pfizer or its designated representative.

Reporting period

For each patient, the safety event reporting period begins at the time of the patient's first dose of tafamidis or the time of the patient's informed consent if s/he is being treated with tafamidis at study start, and lasts through the end of the observation period of the study, which must include at least 28 calendar days following the last administration of a drug under study; a report must be submitted to Pfizer Safety (or its designated representative) for any of the types of safety events listed in the table above occurring during this period. If a patient was administered a drug under study on the last day of the observation period, then the reporting period should be extended for 28 calendar days following the end of observation. Most often, the date of informed consent is the same as the date of enrollment. In some situations, there may be a lag between the dates of informed consent and enrollment. In these instances, if a patient provides informed consent but is never enrolled in the study (e.g., patient changes his/her mind about participation, failed screening criteria"), the reporting period ends on the date of the decision to not enroll the patient.

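### Follow-up ends when tafamidis is stopped, although the quality-of-life, hospitalisation and death outcomes are set over 24 months from the index date

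*Protocol*

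**What the plan says.** Section 9.1 follows patients from the index date (first prescription of tafamidis) to the earliest of five events: death, withdrawal from the study, and then "iii) have terminated of treatment, iv) have been lost to follow up, or, v) finalize the 24 months of following up". The Abstract gives the same list: "iii) have terminated of treatment, iv) have been lost to follow up, or v) finalize the 24 months of following up". Termination of treatment is not defined.

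The objectives and setting use a different time frame. The primary objective in Section 8 is "To describe the impact of tafamidis use in Colombian patients diagnosed with ATTR-CM on quality of life during two years of follow-up". Section 9.2 states: "The follow-up period is 24 months since index date with measurement every three months". It continues: "During this period quality of life, hospitalization frequency, and death will be measured. The endpoint of the study will be death". Section 7 likewise says that the study means to measure quality of life, hospitalisation and mortality over the first two years.

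Three other sections bear on the point:
- Section 9.7.1 describes hospitalisation only over the period of treatment exposure.
- Section 9.7.4 rules out imputation and uses observed cases.
- Section 11 sets the safety reporting period to run through the end of observation, "which must include at least 28 calendar days following the last administration of a drug under study".

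**The concern.** The two-year outcomes need two years of observation, but the follow-up rule withdraws it from one group of patients, those who stop the drug. If people stop because they are doing badly, the patients who remain at month 24 are a favourable selection, and the mean KCCQ, the hospitalisation count and the number of deaths all look better than they are for the cohort as enrolled. If people stop for unrelated reasons, the selection may do little harm. The data that would tell these cases apart are the data not collected. No later analysis plan can recover interviews that were never held.

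The text also leaves unsettled which quantity is intended: two-year outcomes in everyone who started (Sections 7, 8 and 9.2), or outcomes while on drug (Section 9.7.1 for hospitalisation, and in effect Section 9.1 for everything).

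**Working it through.** **The sections side by side.** The protocol gives no stopping rate, power or event figure on this point, and Section 9.5 says that no sample size is required, so there is no stated figure to reproduce.

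1. After termination of treatment, KCCQ collection ends, because Section 9.1 ends follow-up and no other section schedules a call.
2. Hospitalisations and deaths remain visible for a time. Section 11 classes both as serious adverse events, records all of these on the case report form, and covers 28 days after the last dose. Beyond that it adds only events that the investigator learns of after study completion and considers related to tafamidis.
3. Month-24 summaries on observed cases therefore contain only patients still on treatment.

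**Illustration for KCCQ.** Let p be the share of month-24 survivors who have stopped, and g the amount by which their mean score lies below that of continuers. The mean over all survivors is (1 − p) × continuers + p × stoppers. The observed mean is that of continuers alone. The difference is p × g. Neither p nor g is in the documents; both are assumed.

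| p | g = 5 | g = 10 | g = 20 |
|---|---|---|---|
| 10% | 0.5 | 1.0 | 2.0 |
| 20% | 1.0 | 2.0 | 4.0 |
| 30% | 1.5 | 3.0 | 6.0 |

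Section 9.3.1 takes 5 points as a small but clinically important change. With g = 20, p × g exceeds 5 only if p > 5/20 = 25%. With p = 30%, it does so only if g > 5/0.30 = 16.7. Only that corner of the range passes the threshold.

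**Illustration for deaths.** Inputs: 50 patients (Section 9.5); 30-month mortality of 29.5% on tafamidis and 42.9% on placebo in the pivotal trial as reported in Section 7; constant hazards; stopping assumed as above. The on-drug hazard is h = −ln(1 − 0.295)/30 = 0.01165 per month, and the placebo hazard is −ln(1 − 0.429)/30 = 0.01868 per month. The stopping hazard is s = −ln(1 − p)/24. Deaths after stopping are 50 × ∫ s·exp(−(s + h)t)·[1 − exp(−h′(24 − t))] dt over 0 to 24 months, with h′ equal to either hazard.

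| p | patients who stop | deaths on drug | deaths after stopping | of these within 28 days | person-time lost |
|---|---|---|---|---|---|
| 10% | 4.4 | 11.6 | 0.6–0.9 | 0.05–0.07 | 4.9% |
| 20% | 8.8 | 11.0 | 1.2–1.8 | 0.09–0.15 | 9.9% |
| 30% | 13.2 | 10.3 | 1.9–2.8 | 0.14–0.22 | 15.2% |

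These counts run from the index date. Patients must be alive to consent, and collection starts after the index date, so the real numbers would be smaller. What matters is the proportion: under these assumptions the 28-day window catches less than a tenth of the deaths after stopping.

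**The case against.** The strongest defence is that this is a choice of what to describe. The study is single-arm and descriptive, its subject is the use of tafamidis, and Section 9.7.1 openly confines hospitalisation to treatment exposure. A while-on-treatment description is legitimate, and which summary comes first is often left to the analysis plan. That stands as far as it goes. It does not reconcile Section 9.1 with Sections 7, 8 and 9.2, and it does not justify failing to collect data that would permit both summaries.

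Several stronger readings are tempting, but the documents do not support them:
- That the outcomes of stoppers are never seen. Everything up to the stop date is kept, and hospitalisations and deaths stay reportable for 28 days.
- That losing access ends follow-up, which would defeat the objective "To describe the access barriers during the use of tafamidis". Loss of supply is not a listed end event. Section 9.1 treats any supply delay as an access limitation to be assessed during follow-up. The risk is only one of reading: Section 9.3.1 defines discontinuation, for persistence, as the end of the previous supply with no grace period, and someone could carry that definition over to the undefined end of treatment.
- That Section 11 is unworkable beside Section 9.1. Its demand that observation include 28 days after the last dose does clash in wording with a follow-up that ends at termination. But the same section extends the reporting period by 28 days when drug was given on the last day of observation, so safety reporting still functions.
- That Section 10.3 contradicts Section 9.1. It concerns withdrawal from the study, not the end of treatment.
- That sensitivity analyses are lacking. They may sit in an analysis plan that is not at hand.

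It is also fair to say that continued calls cannot recover assessments missed before enrolment. Index dates run from August 2022 to August 2023, while collection starts on 15 November 2023.

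**Conclusion.** The point holds as a cheap improvement to the design. By the protocol's own text, KCCQ after stopping is not collected, nor are hospitalisations and deaths beyond the 28-day safety window, apart from later events considered related to tafamidis. The two-year outcomes in Sections 7, 8 and 9.2 will therefore be answered at month 24 only for patients still on drug.

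The size is uncertain. The 0.5 to 6 point range for KCCQ rests wholly on an assumed 10 to 30% stopping and an assumed gap of 5 to 20 points, and most of that range lies below 5 points. That stoppers do worse is itself an assumption. The case for change rests on the contradiction and on the irrecoverable loss of data, not on a demonstrated large bias.

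**What to change.** - In Section 9.1 and the Abstract, remove termination of treatment from the events that end follow-up. Continue the existing three-monthly calls to month 24 whether or not tafamidis continues, and record the stop date and reason. This alters observation only and implies nothing about treatment.
- Report the two-year results regardless of treatment status, with an on-treatment summary beside them labelled as such. Bring Section 9.7.1 into line for hospitalisation.
- Define termination of treatment, and state that a supply gap counted as discontinuation under Section 9.3.1 does not by itself end follow-up.
- Reconcile the end of follow-up in Section 9.1 with the observation-period wording in Section 11.

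The cost is a protocol amendment and a few calls per patient who stops: at most 24/3 = 8 for someone who stops before month 3, and fewer for later stops. At 10 to 30% stopping this concerns about 4 to 13 of 50 patients.

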- Comorbidities (Heart failure at early age, any cardiac arrhythmias or conduction disorders, type of any cardiac arrhythmias or conduction disorder, diabetes mellitus, hypertension, sleep apnea, chronic kidney diseases, intracardiac thrombosis, stroke, polyneuropathy, orthostatic hypotension, erectile dysfunction, glaucoma)
- Adherence
- Persistence
- Hospitalization
- Quality of Life (KCCQ-OS)
- Cardiovascular functionality (6-MWT and scintigraphy)
- Hospitalization
- **Data sources**

There will be several sources of information. From the medical record provided by the patient will be abstracted the demographic and clinical characteristics related to diagnosis, comorbidities, and treatment at baseline, as well as the previous medications to manage CA. Other sources will be the patient to confirm or complete the information associated with it.

The study will be performed in approximately 6 Colombian Health Provider Institution (IPS, in its Spanish acronym) whose population includes patients with ATTR-CM diagnosis in the period established. These sites will be in four Colombian cities (Bogotá, Medellin, Cali, and Barranquilla) which have a cardiologist with experience in diagnostic and management of ATTR-CM.

During the follow-up, the patient will provide the information about changes in the treatment, issues to supply tafamidis, and hospitalization which can be confirmed with the summary of the medical records of the patient. The quality of life will be measured using the KCCQ scale through call or face to face meeting. 6-MWT and scintigraphy will be abstracted from medical records.

- **Study size**

Sample size is not required for being observational and descriptive study. The expected number of patients eligible for the study is close to fifty considering the number of patients identified with the diagnosis and the access to the treatment.

PFIZER CONFIDENTIAL

CT24-WI-GL02-RF01 6.0 Non-Interventional Study Protocol Template For Primary Data Collection Study 01-

Aug-2023

Page 14 of 57

**CLINICAL AND MEDICAL CONTROLLED DOCUMENT (CMCD)
REQUIRED FORM/TEMPLATE**

Identifier	Version	Title	Effective Date
CT24-WI-GL02-RF01	6.0	NON-INTERVENTIONAL STUDY PROTOCOL TEMPLATE FOR PRIMARY DATA COLLECTION STUDY	01-Aug-2023

• **Data analysis**

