Any cardiac arrhythmias or conduction disorders	Clinical characteristic	Medical record, Interview	Yes, No
Type of any cardiac arrhythmias or conduction disorders	Clinical characteristic	Medical record, Interview	Cardiac arrhythmias, Cardiac arrest, Paroxysmal tachycardia, Atrial fibrillation and flutter, Conduction disorders, Atrioventricular and left bundle branch block, other conduction disorders
Lumbar spinal stenosis	Clinical characteristic	Medical record, Interview	Yes, No
Hypertrophic cardiomyopathy over 60 years old	Clinical characteristic	Medical record, Interview	Yes, No
Embolic stroke	Clinical characteristic	Medical record, Interview	Yes, No
Low flow/low gradient aortic valve stenosis	Clinical characteristic	Medical record, Interview	Yes, No
Diabetes mellitus	Clinical characteristic	Medical record, Interview	Yes, No
Hypertension	Clinical characteristic	Medical record, Interview	Yes, No
Sleep apnea	Clinical characteristic	Medical record, Interview	Yes, No
Chronic Kidney Diseases	Clinical characteristic	Medical record, Interview	Yes, No
Any cardiovascular device	Clinical characteristic	Medical record, Interview	Yes, No
Which any cardiovascular devices	Clinical characteristic	Medical record, Interview	Cardiac resynchronization

PFIZER CONFIDENTIAL

CT24-WI-GL02-RF01 6.0 Non-Interventional Study Protocol Template For Primary Data Collection Study 01-

Aug-2023

Page 25 of 57

**CLINICAL AND MEDICAL CONTROLLED DOCUMENT (CMCD)
REQUIRED FORM/TEMPLATE**

Identifier	Version	Title	Effective Date
CT24-WI-GL02-RF01	6.0	NON-INTERVENTIONAL STUDY PROTOCOL TEMPLATE FOR PRIMARY DATA COLLECTION STUDY	01-Aug-2023

			therapy – defibrillator (CRT-D), Cardiac resynchronization therapy – pacemakers (CRT-P), implantable cardioverter defibrillator (ICD)
History of heart block	Clinical characteristic	Medical record, Interview	Yes, No
NYHA FC	Clinical characteristic	Medical record, Interview	I, II, III, IV
Syncope	Clinical characteristic	Medical record, Interview	Yes, No
Carpal tunnel syndrome	Clinical characteristic	Medical record, Interview	Yes, No
Bleeding history	Clinical characteristic	Medical record, Interview	Yes, No
Intracardiac thrombosis	Clinical characteristic	Medical record, Interview	Yes, No
Stroke	Clinical characteristic	Medical record, Interview	Yes, No
Polyneuropathy	Clinical characteristic	Medical record, Interview	Yes, No
Orthostatic hypotension	Clinical characteristic	Medical record, Interview	Yes, No

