9.3.1. Definitions

Kansas City Cardiomyopathy Questionnaire (KCCQ) Score: It is a Patient-reported outcome composed by 23-item, KCCQ that takes 4-6 min to complete. A self-administered questionnaire will be used to measure the patient's perception of their health status within a 2-week recall period. The domains of this scale are: Symptom, Physical function, Social Limitation, self-efficacy, Symptom stability, and Quality of Life. The clinical summary is calculated including the domain Physical limitation and Symptoms. The overall summary score combines total symptoms, physical and social limitation, and Quality of life. The score for each domain has a range from 0-100 where 0 is considered worst health and 100 the best health. Changes in the Overall summary of 5, 10 and 20 points have been considered small but clinically important, moderate to large, and large to very large changes, respectively (12). The scale has been translated and validated to Spanish of Colombia (15).

Perugini grading scale: It is a semi-quantitative method of scoring cardiac uptake following injection of 99mTc-DPD, 99mTc-Pyrophosphate or 99mTc-HMDP scintigraphy (16). It is classified as:

- grade 0: no cardiac uptake and normal rib uptake
- grade 1: cardiac uptake which is less than rib uptake
- grade 2: cardiac uptake with intensity similar rib uptake
- grade 3: cardiac uptake greater than rib uptake with mild or absent rib uptake

6 Minute walk test: It is considered as an alternative to cardiopulmonary exercise test for risk stratification in patients with Heart Failure. It is a simple test that requires no specialized equipment or physicians. It assesses the functional capacity while the patient walks on a flat, solid surface in a period of 6 min (13).

Hospitalization: It is defined as a nonelective admission to an acute care setting for medical therapy that results in at least a 24-hour stay (17).

Cardiovascular causes of hospitalization: The following diseases were considered as cardiovascular causes of hospitalization only it was considered the primary diagnosis (17):

- Heart failure
- Arrhythmia: When the patient is hospitalized by bradyarrhythmia, atrial, or ventricular rhythm disorders of the heart.
- Transient ischemic attack
- Stroke

PFIZER CONFIDENTIAL

CT24-WI-GL02-RF01 6.0 Non-Interventional Study Protocol Template For Primary Data Collection Study 01-

Aug-2023

Page 29 of 57

**CLINICAL AND MEDICAL CONTROLLED DOCUMENT (CMCD)
REQUIRED FORM/TEMPLATE**

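### The change-from-baseline objective for cardiovascular functionality has no baseline 6-minute walk value, counts tracer uptake as function, and gives contradictory source and timing

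*Protocol*

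**What the plan says.** Section 8 lists as a secondary objective "To outline the change in baseline for patients in cardiovascular functionality in patients prescribed tafamidis". The exploratory objective relates baseline variables to "changes of quality of life and cardiovascular functionality". The outcome is defined in the variable list of the abstract: "Cardiovascular functionality (6-MWT and scintigraphy".

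On how the two tests arise, Section 9.1 says "The 6 min walk test (6MWT) and scintigraphy will be conducted based on the decision of cardiologist or responsible physician", and then "They will be abstracted from medical records of patients who had measured them". Section 9.2 abstracts both from the medical record over the period of the study. In Table 1 both rows are empty, with a footnote that the physician may choose another test. Table 2 lists 6MWT once, in metres, as an outcome. It lists the Perugini grade twice, at diagnosis and as an outcome.

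Section 9.1 also says that "the data related to hospitalizations, cardiovascular functionality, quality of life will be collected directly from the patients using validated questionnaires and structured interviews", and that functionality is measured 24 months after the prescription. Section 9.3.1 says of the Perugini scale: "It is a semi-quantitative method of scoring cardiac uptake following injection". It describes the 6MWT as assessing functional capacity.

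**The concern.** A change from baseline needs a measure of the thing named, a value before treatment, a later value, and dates for both. The protocol does not secure these for cardiovascular functionality. One of its two components is not a measure of function by the protocol's own definition. The other has no baseline variable and no test date.

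Followed as written, the study would report functional change from whatever tests clinical care happened to produce, with no common starting point, beside an imaging grade under the same label. The exploratory objective inherits the problem. A later analysis plan can set windows and pairing rules, but it cannot recover a baseline value or a test date that the case report form never collected.

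**Working it through.** The protocol states no figure for this objective (no testing rate, variability or target number), so there is nothing to reproduce. The check sets the sections side by side.

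| Question | One place | Another place |
|---|---|---|
| What is functionality? | Abstract: 6MWT and scintigraphy | 9.3.1: 6MWT is functional capacity; Perugini grade is tracer uptake relative to rib, 0 to 3 |
| Source? | 9.1: patients, by questionnaire and interview | Later in 9.1, 9.2 and 9.4: abstracted from medical records |
| When? | 9.1: 24 months after prescription | Table 1: no visit marked, month 24 included; 9.2: any time in the study |
| Baseline 6MWT? | Section 8: change from baseline | Table 2: one 6MWT row, an outcome, with no baseline entry or date |
| Baseline scintigraphy? | Section 8: change from baseline | Table 2: grade at diagnosis, not tied to the index date (first prescription) |

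**Baseline.** Table 2 shows how a before-and-after pair is written elsewhere: the QRS sums and the Sokolow-Lyon index each have a row at diagnosis and a row at the end of follow-up. 6MWT has no such pair. The collection period in 9.2 does not supply one. Whether it means the data-collection period (from 15 November 2023, Section 6) or follow-up from the index date, a walk test done before the prescription falls outside it. Patients were treated between August 2022 and August 2023 (9.2).

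**Analysis.** Section 9.7.5.2 plans, if feasible, mixed models with visit as a fixed effect. Functionality has no scheduled visits to enter. Section 9.7.4 uses observed cases without imputation.

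**Scale, for illustration.** Inputs: N = 50 (9.5 expects close to fifty; 9.2 says fewer) and assumed shares of patients with both a baseline and a follow-up test. Number of pairs: n = 50 × share. The 95% confidence interval half-width for a mean change, in standard deviations (SD) of the change, is t(0.975, n−1)/√n.

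| Assumed share paired | n | Half-width |
|---|---|---|
| 100% | 50 | 2.010/√50 = 0.28 SD |
| 80% | 40 | 2.023/√40 = 0.32 SD |
| 50% | 25 | 2.064/√25 = 0.41 SD |
| 30% | 15 | 2.145/√15 = 0.55 SD |
| 20% | 10 | 2.262/√10 = 0.72 SD |

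If testing at the two times were independent with probability a each, expected pairs are 50a²: 32 for 80%, 18 for 60%, 12.5 for 50% and 4.5 for 30%.

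**Selection.** Suppose being tested correlates ρ with the change, under a normal selection model with share p tested. The observed mean then shifts by ρ × φ(c)/p, with c = z(1−p).
- p = 50%: φ(0)/0.5 = 0.798, so ρ = 0.2 to 0.5 gives 0.16 to 0.40 SD.
- p = 30%: φ(0.524)/0.3 = 1.159, so the same ρ gives 0.23 to 0.58 SD.

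Neither ρ nor the testing rates come from the protocol.

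**The case against.** The study is non-interventional and descriptive. It cannot require a test, so the empty rows in Table 1 are deliberate and footnoted. Section 9.9 discloses limited availability, and 9.7.4 says missing data will be reported. All of this stands. The absence of mandated tests is no fault, and a reader who infers that the objective cannot be answered goes too far: change can be outlined in patients with paired results.

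Three further inferences also lack support:

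- *Repeat tests occur mainly in patients still able to walk or under work-up.* The sentence in 9.1 goes on to refer to institutional guidelines and medical practice, so testing may follow a routine. The direction of any selection is unknown.
- *An unchanged Perugini grade will be read as preserved function.* Table 2 keeps grade and metres as separate outcomes, and nothing combines them. The label invites the reading but does not make it.
- *NYHA class is not repeated because it lacks the per-visit asterisk.* KCCQ and hospitalization lack it too and are repeated in Table 1, while the glomerular filtration rate at diagnosis carries it. The asterisk is not a reliable guide.

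It can also be said that 9.1 promises to collect earlier information for patients already on treatment. That sentence is general, relies on what patients provide, and has no matching 6MWT field in Table 2. Baseline windows can indeed wait for an analysis plan; the variable itself cannot.

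**Conclusion.** The point holds in a limited form. On the protocol's own text, the objective names a functional change but includes an uptake grade, has no baseline or dated 6MWT, and carries two contradictions, on source and on timing. What is lost is an interpretable change from baseline for the cohort. A description in the tested subset remains possible.

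The size is uncertain because the protocol gives no testing rates. With an assumed 30% to 60% paired, change is known in 15 to 30 of about 50 patients. At 15 pairs the interval is about twice as wide as with full testing (0.55 against 0.28 SD), before any selection effect. The textual findings need none of these assumptions. One secondary and one exploratory objective are affected; the primary quality-of-life objective is not.

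**What to change.** 1. In Table 2, split 6MWT into a dated baseline value (last recorded test before the first tafamidis dose, from the medical record) and dated follow-up values. Widen the abstraction period in 9.2 to match.
2. Limit the objective to patients with paired 6MWT results. Report how many were tested, and compare tested with untested patients on baseline characteristics.
3. Take the Perugini grade out of cardiovascular functionality and report it separately as imaging or amyloid uptake.
4. Reconcile the source and 24-month statements in 9.1, and the matching text in the abstract, with the record abstraction in 9.1, 9.2 and 9.4 and the unscheduled rows of Table 1.

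The cost is protocol wording, a few case report form fields and some record abstraction. No procedure is added.

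An optional, cheap supplement is to record NYHA class at each existing three-monthly contact and report the KCCQ Physical Limitation score. Neither should replace the definition. KCCQ starts only after consent, so most patients have no pre-treatment value. The domain is already part of the KCCQ overall summary, the primary outcome. NYHA class by telephone is less precise than in clinic. The report should state all three limits.
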